**University of Florida IRB-01
Protocol**

Title: A sociolinguistic-enabled web application to develop precision health intervention for African Americans

Investigators: [name] (PI), [name], [name], [name], , [name], [name], [name]

1. Abstract:

This pilot study will explore the preliminary efficacy of a colorectal cancer (CRC) screening intervention delivered by virtual health assistants (VHAs). Participants will include 750 patients in the US between the ages of 45 and 75 recruited through Qualtrics panels: 375 who are non-adherent to CRC screening guidelines, and 375 patients who are adherent to CRC screening guidelines. The main research question is: How does the integration of different levels of dialect density of the linguistic features of African American English (AAE) influence the perceived credibility of a Black VHA? Four types of VHAs will be presented to our patients: a VHA with Standardized American English (SAE) linguistic features, a VHA with a low level of African American English (AAE) linguistic features integrated, a VHA with a high level of African American English (AAE) linguistic features integrated, and a text-only control condition. Survey questions will be used to obtain credibility judgments about VHAs post-interaction.

2. Background:

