Interventions that use tailored messages are effective for improving CRC screening. However, two important questions must be answered before tailored screening interventions can be implemented in healthcare systems. One is the degree to which message content must be tailored to be effective and another is how to effectively engage participants. The current project is an extension of an existing project that uses mobile virtual human technology (VHT) to deliver tailored CRC screening messages for African Americans to improve screening within guidelines. Interventions using VHT offer numerous advantages, including the capability to be customized to the linguistic preferences of the patient. As such, the use of virtual technology could help reduce CRC screening barriers such as cultural mismatch and low self-efficacy among African American patients.

The purpose of this proposal is to investigate to what extent the incorporation of AAE linguistic features increases, decreases, or has no effect on the perceived credibility of VHAs. This pilot study is meant to be exploratory in nature. We seek to explore the following specific aim:

- Examine how tailoring the dialectal variety of the speech of VHAs influences their perceived credibility. **Approach:** Each participant will interact with a VHA that differs in speech containing

either: (1) strictly linguistic features of SAE, (2) a low level integration of AAE linguistic features, (3) a high level integration of AAE linguistic features, or (4) a voiceless, text-only control. Post-interaction, participants will be asked to judge how credible they felt the VHA was through survey questions.

4. Research Plan:

6.1. Pilot study design. This pilot study will use a posttest-only, 3 (SAE: Standardized American English / low level AAE: African American English / high level AAE) x 2 (Introduction / No introduction) with a control group (i.e., no voice) randomized experimental message design. Patients (N=750) will be recruited from a national panel by Qualtrics. In order to be included in the study, participants must be between the ages of 45-75, and have health insurance. We will recruit equal numbers of male and female patients.

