After providing informed consent, participants will be randomly assigned to a VHA. Participants will be assigned at random to a Black, gender-matched VHA that speaks SAE, AAE (low level), or AAE (high level). Each VHA will also either include an introduction from the voice actor/actress or will not include an introduction. The control group will be the same intervention content delivered via text-only (e.g., photos of the Black VHA). After completing the intervention, participants will complete a questionnaire with dependent measures and potential mediators. This questionnaire will solicit participant opinion on the credibility of the VHA and also gauge the participant's intent to screen for CRC. Participants will receive monetary compensation which will be credited to their Qualtrics member account on the site.

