Descriptive statistics for credibility score including mean, standard deviation, median, and inter-quartile range (IQR) will be calculated (1) in the overall study cohort and (2) within each of the 7 groups. Similarly, descriptive statistics for intention to CRC screen including frequency and proportion will be calculated (1) in the overall study cohort and (2) within each of the 7 groups. Such information will serve as preliminary estimates to facilitate future powered studies. We will also generate descriptive statistics of collected demographic and clinical variables (e.g., age, gender, etc.). Graphical illustration will be provided if applicable. One-way ANOVA or Kruskal-Wallis test will be used to test difference of credibility score among 7 groups and two-sample t-test or Wilcoxon rank sum test will be used for post-hoc pairwise comparison. Chi-squared test or Fisher exact test will be used to test difference of intention to CRC screen among 7 groups and pairwise comparison. As this is a pilot study, all statistical analysis is exploratory. Therefore, multiple comparison adjustment will not be considered.

6.8. Patient-centeredness. The proposed intervention will test different levels of linguistic variation. To maximize patient centeredness, the investigators will conduct formative research with members of the intended patient population during the period in which the current study is under review at NCATS. The co-PI ([name]) currently has an open protocol in which focus groups are being used to ensure patient acceptability of all aspects of the VHAs. For more details on focus group procedures, please see our recent manuscript published in *Psycho-Oncology* (see [name] et al., 2020). [name] will conduct additional focus groups to examine patient perceptions of the different levels of linguistic variation and use this feedback to finalize how the stimuli are presented in the experiment to maximize patient centeredness.

5. Possible Discomforts and Risks:

- As with any behavioral intervention, there is the possibility of minimal emotional discomfort from being presented with individual risk factors for a disease. However, the probability of any physical, psychological, or social harm is minimal to none.

Adverse Event Reporting

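### The design crosses dialect with introduction, but section 6.7 analyses seven unordered groups and commits to no dialect effect averaged over introduction and no interaction

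*Combined protocol and SAP*

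**What the plan says.** Section 6.1 describes three dialect levels (SAE, low AAE, high AAE) "x 2 (Introduction / No introduction) with a control group (i.e., no voice) randomized experimental message design". Introduction is a second manipulated factor: "Each VHA will also either include an introduction from the voice actor/actress or will not include an introduction". That makes 3 × 2 + 1 = 7 groups, which matches the count in section 6.7.

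The scientific question concerns one of the two factors. The Abstract asks "How does the integration of different levels of dialect density of the linguistic features of African American English (AAE) influence the perceived credibility" (here, that of the virtual health assistant, VHA), and the single aim in section 3 is "Examine how tailoring the dialectal variety of the speech of VHAs influences their perceived credibility". Section 6.6 makes the credibility score the primary outcome.

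For that outcome, section 6.7 plans descriptive statistics overall and in each of the seven groups, and then: "One-way ANOVA or Kruskal-Wallis test will be used to test difference of credibility score among 7 groups". Two-sample t or Wilcoxon tests follow for pairs of groups. Intention to screen is handled in the same way with chi-squared or Fisher tests. Everything is declared exploratory and unadjusted for multiplicity. The stated use of the descriptive results is: "Such information will serve as preliminary estimates to facilitate future powered studies".

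Neither section 6.7 nor any other section mentions a two-way model, a dialect effect averaged over introduction, an introduction effect, an interaction or a planned contrast.

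**The concern.** The planned analysis does not use the structure that the randomisation creates. A 6-df test over seven groups mixes three questions: dialect, introduction, and voice versus text. A significant result is a correct answer to whether any group differs, but it says nothing specific about dialect.

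The pairwise tests do reach dialect, but only within one introduction level at a time. Each dialect comparison therefore gets two half-sample answers. Nothing in the plan combines them, and nothing tests whether they differ.

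A later powered study would want one dialect effect with its precision, and some indication of whether introduction changes it. The plan commits to neither. The choice between averaging and reporting a single cell pair is left until the results are known. If one of the two tests is significant and the other is not, this can be misread as an interaction.

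**Working it through.** **Inputs.** N = 750 (section 6.1), set by budget (section 6.7), so there is no sample-size formula to reproduce. The documents give no allocation ratio, SD, alpha or effect size. Assumptions: SD = 1 in every cell, two-sided 5% tests, equal voiced cells, and two allocations.

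- A, seven equal groups: n = 750/7 = 107.1 per cell, or 214.3 per dialect level.
- B, equal split over the Abstract's four conditions ("Four types of VHAs will be presented to our patients"): 750/4 = 187.5 per condition, so n = 93.75 per voiced cell and 187.5 text-only.

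**Pairs of groups.** There are 7 × 6 / 2 = 21:

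- dialect differs, introduction the same: 3 × 2 = 6
- introduction differs, dialect the same: 3
- both differ: 3 × 2 = 6
- one member is the control: 6

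**Precision.** With n per voiced cell, the variance is 2/n for one dialect pair, 1/n for the same comparison averaged over introduction, and 4/n for one interaction contrast (difference of two differences). The first to the second is 2:1 for any n.

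| | A | B |
|---|---|---|
| SE, one pair, √(2/n) | 0.137 | 0.146 |
| SE, averaged, √(1/n) | 0.097 | 0.103 |
| SE, interaction, √(4/n) | 0.193 | 0.207 |
| 95% half-width, pair / averaged / interaction (1.96 × SE) | 0.27 / 0.19 / 0.38 | 0.29 / 0.20 / 0.40 |
| Detectable at 80% power, pair / averaged (two-sample t) | 0.385 / 0.27 | 0.41 / 0.29 |
| Detectable at 80% power, interaction ((1.96 + 0.84) × SE) | 0.54 | 0.58 |

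**Power and chance disagreement.** Let the true dialect difference be d at both introduction levels (no interaction), and let p be the power of one pair. The two pairs use different participants, so the chance that exactly one is significant is 2p(1 − p). At d = 0.3 under A this is 2 × 0.589 × 0.411 = 0.484.

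| d (SD) | A: pair | A: averaged | A: disagree | B: pair | B: averaged | B: disagree |
|---|---|---|---|---|---|---|
| 0.1 | 11% | 18% | 20% | 10% | 16% | 19% |
| 0.2 | 31% | 54% | 43% | 27% | 49% | 40% |
| 0.3 | 59% | 87% | 48% | 53% | 83% | 50% |
| 0.4 | 83% | 98% | 28% | 78% | 97% | 35% |
| 0.5 | 95% | >99% | 9% | 93% | >99% | 14% |

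**Seven-group test with no dialect effect.** Noncentral F, 6 and 743 df.

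- Text-only alone differs by 0.3 SD: noncentrality 0.09 × n_c × 6n/(6n + n_c) is 8.27 (A) or 12.66 (B), and the test is significant 54% or 76% of the time. At 0.1 SD this is 9% or 11%.
- Introduction alone shifts credibility by 0.3 SD, control midway: noncentrality 6n × 0.15² is 14.46 or 12.66, giving 82% or 76%. At 0.1 SD this is 12% or 11%. With the control at the no-introduction mean, the 0.3 SD figures are 88% or 86%.

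**Seven-group test with a dialect effect.** If credibility rises linearly by 0.3 SD from SAE to high AAE, with no introduction effect and the control at the voiced mean, the 6-df test has 62% (A) or 55% (B) power. A 2-df dialect test has 80% or 74%.

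**The case against.** The strongest reply is that nothing is lost. Section 6.7 promises the mean and SD in every group. With the cell sizes, these give the averaged dialect contrast, the interaction and their standard errors by arithmetic. This is correct, so the fault lies in what is pre-specified and reported.

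A second reply is that six of the planned pairs are legitimate dialect comparisons, and that the seven-group test is never described as a dialect test. Both points stand. The text-only arm is also one of the conditions listed under the aim, so differences from it are of interest. The criticism is that these tests are not matched to the dialect question. They are not invalid.

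Third, the disagreement and omnibus percentages depend on the assumed effect. Disagreement cannot exceed 50%, and it comes close to that at 0.3 SD; the tables show it falling for small and large effects. The 2:1 variance ratio does not depend on any effect size.

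Fourth, a later study may use only one introduction format, in which case the cell results are the relevant inputs, and an average is a clean summary only when interaction is small. That is a reason to report simple effects and interaction beside the average. Exploratory status explains the absent sample-size calculation and multiplicity adjustment, but a pilot meant to supply estimates still needs to say which dialect estimate it will supply.

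**Conclusion.** The concern holds and should be fixed. The plan randomises a crossed design to study dialect, yet commits to no estimate of the dialect effect that uses the crossing and to no estimate of the interaction. Each planned dialect comparison uses about 188 to 214 participants where about 375 to 429 are available, and its variance is doubled. The ratio assumes equal factorial cells and equal variance. At an assumed 0.3 SD effect without interaction, this is 59% against 87% power, or 53% against 83%, depending on allocation.

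No figure in the plan is wrong, no planned test is invalid, and the missing contrasts can be recovered from the cell summaries, so the severity is moderate.

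**What to change.** In section 6.7, keep the seven-group descriptive table and make the main credibility analysis one linear model over the seven cells, with these planned contrasts and 95% confidence intervals:

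1. Dialect averaged over introduction (2 df), reported as low versus SAE, high versus SAE and high versus low.
2. Introduction versus none, averaged over dialect.
3. Dialect by introduction (2 df), with the dialect effects at each introduction level always shown.
4. Text-only control versus the voiced arms, as a separate contrast.

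Keep a rank-based analysis as a sensitivity check if credibility is clearly non-normal. Apply the same contrasts to intention in a model suited to its scale (logistic if binary). Keep the exploratory label.

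The cost is wording only, with no added participants or data. The drawback is that the averaged effect must be read together with an imprecise interaction: for high versus SAE, the 95% half-width is about 0.38 to 0.40 SD, and 80% power is reached only from about 0.54 to 0.58 SD. The plan should say that a non-significant interaction does not show the dialect effect to be the same with and without an introduction.

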6.3. Informed consent process

The first page of the Qualtrics survey will display the information outlined in the informed consent form document. Specifically, the following passage will be included on this informed consent page, "Completion and return of the survey implies that you have read the information in this form and consent to take part in the research. Please keep this form for your records or future reference."

6.4. Timeline. The proposed pilot study is funded through the CTSI. As such, the study team is required to receive UF IRB approval prior to the procedures being submitted to NCATS for additional review. The additional review required by NCATS is expected to take two months. Thus, it is important for the study team to receive SRMC approval for the randomized message design experiment that was funded by the CTSI as soon as possible.

6.5. Stimuli. The speech of the VHA will be manipulated by varying its Dialect Density Measure (DDM) which is the number of dialectal features that are specific to AAE within an utterance in proportion to the number of words spoken in that given utterance. At the pronunciation level, this may include features such

as -g dropping, as in, "I'm gettin' a cold." At the grammatical level, this may include features such as the zero copula/auxiliary ("be" verb) as in, "How you feeling today?"

The scripts with different levels of dialectal density will be read by professional voice actors/actresses. Specific instructions and speech samples illustrating our target AAE features will be provided to the voice actors to ensure a natural and native production of AAE. The instructions will be designed by our team's linguists who have experience conducting linguistic fieldwork and communicating with laypeople without using technical terminologies.

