- The data is collected by Qualtrics, so we will not have any direct contact with participants. The adverse event we will potentially encounter is someone sharing something concerning in the written feedback section. If this occurs, we will contact Qualtrics so they can reach out to the participant.

Data Sharing Plan

- We will share data associated with the trial by depositing these data in Dropbox, a file sharing system approved by UF Integrated Risk Management and providing access to the relevant files with outside investigators. Data include participant responses to survey questions and information about participant interactions with the intervention. Data are deidentified by Qualtrics and we do not have access to anything personally identifiable for participants.
- Data will be shared with investigators working at other accredited universities for the purposes of analysis. The names and Institutions of persons either given or denied access to the data, and the bases for such decisions, will be recorded. Participants will acquire IRB approval from their home institution to review data.

6. Possible Benefits:

- There are no direct benefits from participating in this study. However, participants may have garnered valuable information on their individual risk of developing colorectal cancer. They also learned how to screen for colorectal cancer.

7. Conflict of Interest:

- There are no real or potential conflicts of interest in regards to this research project for any members of the study team.

8. Bibliography

Aune, R. K., & Kikuchi, T. (1993). Effects of Language Intensity Similarity on Perceptions of Credibility Relational Attributions, and Persuasion. *Journal of Language and Social Psychology*, 12(3), 224–238.

Baugh, J. (2018). *Linguistics in pursuit of justice*. Cambridge University Press.

Bourhis, R. Y., & Giles, H. (1977). The language of intergroup distinctiveness. In H. Giles (Ed.), *Language, ethnicity and intergroup relations* (pp. 119–135). Academic Press.

Bourhis, R. Y., Roth, S., & MacQueen, G. (1989). Communication in the hospital setting: a survey of medical and everyday language use amongst patients, nurses and doctors. *Social science & medicine* (1982), 28(4), 339–346. [https://doi.org/10.1016/0277-9536\(89\)90035-x](https://doi.org/10.1016/0277-9536(89)90035-x)

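### Does Section 6.7 need per-arm counts of people randomised and lost, given that credibility is rated only after exposure to the assigned voice?

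*Combined protocol and SAP*

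**What the plan says.** Section 6.1 sets out the design: "This pilot study will use a posttest-only" experiment with three speech levels, each with or without an introduction, plus a text-only control. That makes 3 × 2 + 1 = 7 groups. On size it says "Patients (N=750) will be recruited from a national panel by Qualtrics". On order of events it says "After providing informed consent, participants will be randomly assigned to a VHA", and later "After completing the intervention, participants will complete a questionnaire with dependent measures and potential mediators". Section 6.6 names the credibility score as the primary outcome.

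Section 6.7 explains that the study is an exploratory pilot with its size fixed by budget. It lists descriptive statistics for credibility and for screening intention, overall and by group, then a global test and pairwise tests: "One-way ANOVA or Kruskal-Wallis test will be used to test difference of credibility score among 7 groups". It says of the descriptive results: "Such information will serve as preliminary estimates to facilitate future powered studies". It does not mention numbers randomised or lost by group, an analysis population or the handling of missing scores, and no other section does.

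Section 6.3 places the consent information on the first survey page and quotes this sentence from it: "Completion and return of the survey implies that you have read the information in this form and consent to take part in the research". The Data Sharing Plan says the data include "information about participant interactions with the intervention".

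**The concern.** The voice is the randomised factor, and it could also drive people away. Section 2 (B.1) reports that focus groups criticised some voices and linked speech characteristics to credibility, and B.3 leaves open whether the added linguistic features help or harm. Someone who dislikes the assigned voice may close the browser before reaching the credibility items. With no baseline score there is nothing to fall back on, so the 7-group comparison will in practice use those who reached the items. If low raters quit more often in one group, that group's mean is flattered; if high raters quit, it is understated. Without counts by group a reader could not tell whether this had happened, and the group means are meant to inform later, larger studies.

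The consent wording seems to compound this. Section 6.1 puts consent before assignment, while the sentence in Section 6.3 ties it to finishing and returning the survey, after exposure. Read literally, a person who quits has not given the implied consent, which leaves unclear whether that person may be counted at all.

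**Working it through.** **Figures in the plan.** The 750 is 375 non-adherent plus 375 adherent participants (Abstract), and the sum holds. It was set by budget, so there is no alpha, power, SD or dropout allowance to reproduce. The allocation ratio is not stated; equal allocation gives 750/7 = 107 per group.

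**Size of a possible bias.** The documents give no break-off rate, so every rate and correlation here is an assumption. Let staying depend on a latent normal variable that has correlation r with credibility, and let d be the share who quit. The completer mean then shifts by r × φ(z_d)/(1 − d) SD, and the bias in a comparison is the difference between the two groups' shifts. Positive r means that low raters quit; a negative r of the same size reverses the sign.

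- φ(z_d)/(1 − d) is 0.109 at d = 0.05, 0.195 at 0.10, 0.274 at 0.15 and 0.424 at 0.25.
- The difference is 0.424 − 0.195 = 0.229 for 10% against 25%, and 0.274 − 0.109 = 0.166 for 5% against 15% (before rounding of the terms).

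| Break-off | r = 0 | r = 0.3 | r = 0.5 | r = 1 |
|---|---|---|---|---|
| 10% v 25% | 0 | 0.07 | 0.11 | 0.23 |
| 5% v 15% | 0 | 0.05 | 0.08 | 0.17 |
| equal | 0 | 0 | 0 | 0 |

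Entries are in SD units.

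**Comparison with sampling error.** With 107 scored per group, the 95% half-width of a pairwise difference is 1.96 × √(2/107) = 0.27 SD. If 750 counts people randomised, 10% and 25% break-off leave 107 × 0.90 = 96 and 107 × 0.75 = 80 scored, and the half-width is 1.96 × √(1/96.3 + 1/80.25) = 0.30 SD. Every bias in the table is smaller than either figure.

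**Effect on nominal significance.** With bias b, standard error s and no true difference, the two-sided 5% test rejects with probability Φ(b/s − 1.96) + Φ(−b/s − 1.96). For 10% against 25%:

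- 107 scored per group (s = 0.137): 13% at r = 0.5 and 39% at r = 1.
- 96 and 80 scored (s = 0.151): 12% at r = 0.5 and 33% at r = 1.

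The second line is the consistent one if 750 means randomised. The r = 1 figures are rough in either case: selection that strong would cut completer variance to about 0.71 and 0.53 of its full value, while the formula keeps the SD at 1.

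**Consent wording, side by side.** Section 6.1 has consent, then assignment. Section 6.3 has information on page one, then a standard implied-consent sentence. Both fit a participant who reads the page and proceeds. The consent page itself is not in the file, so an agree button before assignment may well exist. No estimate or test changes with the way this sentence is worded.

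**The case for a change.** The strongest case for a change is that pilot status excuses the missing power calculation and the lack of multiplicity adjustment, but not missing counts. Retention by group is itself an input that a later trial needs, and selection bias, unlike sampling error, does not shrink as studies grow. The request is modest, and the assigned group of people who quit may be unrecoverable if the survey platform did not store it. A chi-squared test of break-off across the 7 groups could also be informative: simulated power is 0.98 when two groups lose 25% and five lose 10%, and 0.93 for 15% against 5%. If only one group differs it is 0.88 and 0.77.

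Much of this stands. Counts by group are worth having, and the size of a sampling error does not make a bias harmless. But the argument is about good reporting; it identifies no error in the analysis as specified. The power figures rest on gaps of 10 to 15 percentage points that nothing in the documents suggests. A formal break-off test and a sensitivity analysis over assumed missing scores are optional extras in a study that declares all its analysis exploratory. Nor does the Data Sharing Plan settle what is stored: it mentions interaction data but does not say that records of people who quit are kept. That is a practical matter for the study team to confirm with the panel vendor.

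**Conclusion.** No change to the plan is needed. Section 6.7 is silent on participant flow and on what 750 counts, and a competent analyst fills both gaps when writing up a randomised comparison. The planned tests and summaries are not wrong as stated. Whether break-off biases them cannot be known from the documents, and neither can the direction. Under the assumed scenarios with moderate correlation (r of 0.3 to 0.5) the bias is 0.05 to 0.11 SD, against a half-width of 0.27 to 0.30 SD for one comparison, and it is zero if break-off is equal or unrelated to credibility. These figures assume equal allocation, a normal score with SD 1 and the illustrative break-off rates. The results are offered as preliminary estimates from an exploratory pilot, and a later study can weigh them alongside the reported flow. The difference between Sections 6.1 and 6.3 on consent is a wording slip to reconcile when the text is next revised; it affects no result.
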